3.2.7 Pharmacokinetic Evaluations

To evaluate the PK of sirukumab in subjects with RA following long-term treatment, serum samples for the measurement of sirukumab concentrations will be collected according to the Time and Events Schedules.

3.2.8 Immunogenicity Evaluations

To evaluate the immunogenicity of sirukumab in subjects with RA following long-term treatment, serum samples for the detection of antibodies to sirukumab will be collected according to the Time and Events Schedules.

3.2.9 Pharmacodynamic Evaluations

Whole blood and serum samples for the analysis of pharmacodynamic markers will be collected and analyzed for proteins, RNA, and other analytes such as but not limited to microRNAs. The samples will be used to better understand the biology of RA, to provide a biological assessment of the response of subjects to treatment with sirukumab, to analyze responders, to assess loss of response, and to determine if the markers can be used to classify patients as potential responders to treatment.

3.2.10 Pharmacogenetic (DNA) Evaluations

Genetic variation and methylation status of DNA can be an important contributory factor to interindividual differences in drug disposition and response and may also serve as a marker for disease susceptibility and prognosis. Pharmacogenetics research may help to explain interindividual variability in clinical outcomes and identify population subgroups that respond differently to a drug. The goal of the pharmacogenetics component is to collect DNA to allow the identification of genetic factors or methylation patterns that may influence the pharmacokinetics, pharmacodynamics, efficacy, or tolerability of sirukumab and to identify genetic factors associated with RA. DNA samples may be used to help address emerging issues and to enable the development of safer, more effective, and ultimately individualized therapies. For details, see Section 9.5.

3.2.11 Self-Administration

Self-administration of SC products in subjects with RA is common practice and subjects with RA are familiar and comfortable with self-injection. In addition, other biologic agents for the treatment of RA are approved for self-administration at home. For additional details, see Section 6.5.

The SmartJect™ AI platform technology device, referred to as PFS-AI, is a prefilled, spring-powered, single use, disposable device for the SC administration of a single dose of a liquid biologic drug product. The PFS-AI was designed as a platform device for several liquid biologic drug products and has a simple, universal design that is suitable for use by clinicians, caregivers, and patients, including those with hand impairment and pain in the hands and wrists resulting from diseases such as rheumatoid arthritis (RA), and psoriatic arthritis (PsA). The PFS-AI is designed to operate effectively in a number of hand orientations. Since the needle is shielded from sight at all times, the PFS-AI also accommodates those patients with a needle phobia who cannot tolerate seeing injections administered.

3.2.12 Health Economics Data Collection

RA is a chronic, progressive, and disabling condition that significantly diminishes physical functioning and health related quality of life. Loss of physical function in RA patients can significantly affect their ability to work and perform other activities of daily living. Indirect costs, primarily associated with loss of income among persons who have left work or reduced work, contribute substantially to the economic impact on patients, families and society. Approximately half of all newly diagnosed RA patients had to stop working within the ensuing 10 years.^{42,50} Hence, maintaining long-term function with resulting maintenance of productivity and employability is an important therapeutic goal in RA.

Treatment of subjects with RA with sirukumab may have a positive impact on subjects' employability, daily work productivity, and reduced time lost from work, compared among treatment groups. For additional details, see Section 9.7.

4 SUBJECT SELECTION

The inclusion and exclusion criteria for enrolling subjects in this study are described in the following 2 subsections. If there is a question about the inclusion or exclusion criteria below, the investigator should consult with the appropriate Sponsor representative before enrolling a subject in the study.

Deviations from the inclusion and exclusion criteria are not allowed because they can potentially jeopardize the scientific integrity of the study, regulatory acceptability or subject safety. Therefore, adherence to the criteria as specified in the protocol is essential.

4.1 Inclusion Criteria

Each potential subject must satisfy all of the following criteria to be enrolled in the study. Each subject must:

CNTO 136 (sirukumab): Clinical Protocol CNTO136ARA3004 – Amendment 3

1. Have completed the final study agent administrations in the primary study (Week 104 injection in CNTO136ARA3002 or Week 52 injection in CNTO136ARA3003) including all other assessments required for these visits. The subject will then be deemed to have completed participation in those studies and will be eligible to enroll in this long-term extension study.
2. Sign an informed consent form (ICF) indicating that they understand the purpose of and procedures required for the study and are willing to participate in the study.
3. Sign an informed consent form (ICF) for pharmacogenetics research in order to participate in the optional pharmacogenetics component of this study, where local regulations permit. Refusal to give consent for this component does not exclude a subject from participation in this clinical study.

4.2 Exclusion Criteria

Any potential subject who meets any of the following criteria will be excluded from participating in the study. The subject will be excluded if he or she:

1. Withdraws consent and/or discontinues participation in study CNTO136ARA3002 or CNTO136ARA3003.
2. Is pregnant
3. Has active diverticulitis.
4. Has any condition that, in the opinion of the investigator, would make participation not be in the best interest (eg, compromise the well-being) of the subject or that could prevent, limit, or confound the protocol-specified assessments.

4.3 Prohibitions and Restrictions

Potential subjects must be willing and able to adhere to the following prohibitions and restrictions during the course of the study to be eligible for participation:

1. If a woman of childbearing potential, she must remain on a highly effective method of birth control during the study and for 4 months after receiving the last study agent. If she is using hormonal contraceptives, she must use an additional non-hormonal birth control method. The exception to this restriction is if the subject or her male partner is sterilized; this situation does not require birth control. A woman must not donate eggs (ova, oocytes) for the purposes of assisted reproduction during the study and for 4 months after receiving the last dose of study agent.

CNTO 136 (sirukumab): Clinical Protocol CNTO136ARA3004 – Amendment 3

2. Men must use an effective method of birth control during the study and for 4 months after receiving the last dose of study agent. The exception to this is if the subject or his female partner is sterilized. Also, men must not donate sperm during the study and for 4 months after receiving the last dose of study agent.
3. See Section 8.2 for prohibited medications.
4. Must agree not to receive a live virus or live bacterial vaccination during the study. Subjects must also agree not to receive a live vaccine for 4 months after receiving the last administration of study agent.
5. Must agree not to receive an investigational medical device or other investigational drugs.

5 TREATMENT ALLOCATION AND BLINDING

5.1 Treatment Allocation

There will be 2 treatment groups for the duration of this study:

Group 1: Sirukumab 100 mg q2 weeks through Week 156 for subjects who enrolled after completing participation in CNTO136ARA3002 and through Week 208 for subjects who enrolled after completing participation in CNTO136ARA3003.

Group 2: Sirukumab 50 mg q4 weeks through Week 156 for subjects who enrolled after completing participation in CNTO136ARA3002 and through Week 208 for subjects who enrolled after completing participation in CNTO136ARA3003.

After the study becomes open-label, subjects treated with SC sirukumab 100 mg q2 weeks will be offered the option to reduce the sirukumab dose to 50 mg q4 weeks at the investigator's discretion. This decision can be made at the subject's first or second major resupply visit (up until approximately 7 months) after implementation of Amendment 3 at the study site.

5.2 Blinding

To maintain the study blind, the study agent container will have a multipart label with directions for use and other information, but not the identity of the study agent, on each part. One part of the label is designed to be torn off, separated from the study agent container, and attached to the subject's source documents. The rest of the label will remain affixed to the study agent container. Thus, the study agent assigned to a subject will be linked between the container and the subject without breaking the study blind. The study agent kit number will be entered in the electronic case report form (eCRF) or other equivalent data capture method when the drug is administered.

CNTO 136 (sirukumab): Clinical Protocol CNTO136ARA3004 – Amendment 3

The investigator will not be provided with treatment codes, but the codes will be maintained within the IVRS/IWRS, which has the functionality to allow the investigator to break the blind for an individual subject when there is a need based on medical judgment.

The study will remain blinded until the following 3 conditions have been met: the Week 52 DBL occurs in study CNTO136ARA3002, the Week 24 DBL occurs in study CNTO136ARA3003, and the last AI usability substudy subject completes the Week 16 visit or terminates from the study.

The blind should be broken only if specific emergency treatment/course of action would be dictated by knowing the treatment status of the subject. In such cases, the investigator may determine the identity of the treatment from the IVRS/IWRS provider. It is strongly recommended that the investigator contact the Sponsor or its designee if possible to discuss the particular situation prior to unblinding in IVRS/IWRS. Telephone contact with the Sponsor or its designee will be available 24 hours per day, 7 days per week. In the event the blind is broken, the Sponsor must be informed as soon as possible. The date and reason for the unblinding must be documented in the appropriate section of the eCRF, and in the source document. The documentation received from the IVRS/IWRS indicating the code break must be retained with the subject's source documents in a secure manner (eg, sealed envelope) so as not to unblind the treatment assignment to the subject, the study site, or Sponsor personnel. The investigator is also advised not to reveal the study treatment assignment to the subject, the study site, or Sponsor personnel.

Subjects who have had their treatment assignment unblinded are expected to continue to return for scheduled evaluations. Further study agent administrations should be discussed with the study responsible physician.

Additionally, a given subject's treatment assignment may be unblinded to the Sponsor, Institutional Review Board/Independent Ethics Committee (IRB/IEC), and site personnel to fulfill regulatory reporting requirements for SUSARs.

A separate code break procedure will be available for use by Janssen Global Medical Safety (GMS) to allow for unblinding of individual subjects to comply with specific requests from regulatory or health authorities.

6 DOSAGE AND ADMINISTRATION

6.1 Dosing Regimen

Subjects will continue to receive the sirukumab dosing regimen they received at the end of the primary studies (CNTO136ARA3002, CNTO136ARA3003).

Group 1: Sirukumab 100 mg SC at Weeks 0 (administered as the last dose in CNTO136ARA3002 or CNTO136ARA3003), 2, and q2 weeks through Week 156 for subjects who enrolled after completing participation in CNTO136ARA3002 and through Week 208 for subjects who enrolled after completing participation in CNTO136ARA3003.

CNTO 136 (sirukumab): Clinical Protocol CNTO136ARA3004 – Amendment 3

Group 2: Sirukumab 50 mg SC at Weeks 0 (administered as the last dose in CNTO136ARA3002 or CNTO136ARA3003), 4, and q4 weeks through Week 156 for subjects who enrolled after completing participation in CNTO136ARA3002 and through Week 208 for subjects who enrolled after completing participation in CNTO136ARA3003. Between sirukumab injections, placebo SC injections will be administered at Weeks 2, 6, and q4 weeks until the study becomes open-label and placebo injections will be discontinued.

After the study becomes open-label, subjects treated with SC sirukumab 100 mg q2 weeks will be offered the option to reduce the sirukumab dose to 50 mg q4 weeks at the investigator's discretion. This decision can be made at the subject's first or second major resupply visit (up until approximately 7 months) after implementation of Amendment 3 at the study site. Once a subject's dose is reduced to 50 mg q4 weeks, the subject will receive that dose for the remainder of the trial (ie, a return to 100 mg q2 weeks will not be allowed). If a subject opts to remain on the sirukumab 100 mg q2 weeks dose, he or she will remain on that dose for the duration of their participation in the study (ie, the subject will not have the option to reduce the dose at a subsequent timepoint).

If an injection is missed, every effort should be made to have the missed injection administered within 7 days after the scheduled date for that injection. In case it is not possible to administer the missed injection in time, site personnel should discuss the issue with the medical monitor.

After a minimum of 1 year treatment in CNTO136ARA3004 for subjects from study CNTO136ARA3002, or a minimum of 2 years of treatment in CNTO136ARA3004 for subjects from CNTO136ARA3003, and after sirukumab is approved for the treatment of RA in the subject's country of residence, the Sponsor may no longer offer study treatment in CNTO136ARA3004 for those specific subjects. At that point the subject will have the opportunity to discuss treatment options with their treating physician.

For details on self-administration of study agent see Section 6.5.

6.2 Blinding

To maintain the blind, all subjects will receive study agent as 1 SC injection as follows:

Group 1 (sirukumab 100 mg): 1.0 mL sirukumab 100 mg injection q2 weeks.

Group 2 (sirukumab 50 mg): 1.0 mL sirukumab 50 mg injection q4 weeks. Between sirukumab injections, placebo SC injections will be administered at Weeks 2, 6, and q4 weeks until the study becomes open-label and placebo injections will be discontinued.

After the study becomes open-label, subjects treated with SC sirukumab 100 mg q2 weeks will be offered the option to reduce the sirukumab dose to 50 mg q4 weeks at the investigator's discretion. This decision can be made at the subject's first or second major resupply visit (up until approximately 7 months) after implementation of Amendment 3 at the study site.

6.3 Timing and Study Agent Administration

Through the end of the study, it is recommended that both the visit and the SC study agent administration occur within 7 days of the scheduled visit day. The SC study agent administrations must always be at least 7 days apart.

6.4 DMARD/Oral Corticosteroid Initiation/Adjustment

Subjects may adjust or initiate DMARDs and/or oral corticosteroids at the investigator's discretion. Permitted DMARDs include methotrexate (MTX), sulfasalazine (SSZ), hydrochloroquine (HCQ), chloroquine (CQ), and bucillamine.

Prohibited medications listed in Section 8.2 may not be initiated by subjects as long as they are receiving study agent administrations.

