Sirukumab concentration (pharm serum sample) ^{c,d}				X
Antibodies to sirukumab (pharm serum sample) ^{c,d}				X
Ongoing Subject Review				
Injection-site evaluations	X			
Adverse events	X	X	X	X
Concomitant medications	X	X	X	X

a. Subjects who discontinue study agent injections and who are not terminating study participation should return for all scheduled follow-up assessments through approximately 16 weeks after the last study agent injection as specified in this table.
 
b. The first safety and efficacy follow-up visit should occur 4 weeks \pm 14 days after their last study agent injection. The visit window for follow-up assessments is \pm 14 days.
 
c. Pharm serum samples (sirukumab concentration and antibodies to sirukumab) will be collected at the final safety and efficacy follow up visit only from those subjects who had pharm serum samples collected at earlier time points in study CNTO136ARA3002 (approximately 750 subjects randomized in CNTO136ARA3002 before 18 November 2013) and from all subjects enrolled after participating in study CNTO136ARA3003.
 
d. Blood collected from one venipuncture will be divided into 3 serum aliquots (1 each for sirukumab concentration, antibodies to sirukumab and a backup sample). Refer to the Central Laboratory Manual for more detailed instructions.
				

ABBREVIATIONS

ACR	American College of Rheumatology
AE	adverse event
AI	Autoinjector
ALT	alanine aminotransferase
anti-HBc total	hepatitis B core antibody
anti-HBs	hepatitis B surface antibody
AST	aspartate aminotransferase
BD	Becton-Dickinson
BUN	blood urea nitrogen
CDAI	Clinical Disease Activity Index
CEC	Clinical Events Committee
CQ	chloroquine
CRF	case report form
CRP	C-reactive protein
CSR	Clinical Study Report
C _{trough}	Observed serum concentration immediately prior to the next administration
CV	cardiovascular
CYP	cytochrome P450
DAS28	Disease Activity Index Score 28
DBL	database lock
DMARD	disease modifying antirheumatic drugs
DMC	Data Monitoring Committee
DNA	deoxyribonucleic acid
DSUR	Development Safety Update Report
ECG	electrocardiogram
eCRF	electronic case report form
eDC	Electronic Data Capture
EULAR	The European League Against Rheumatism
Fc	fragment crystallizable
FDA	Food and Drug Administration
G	gauge
GCP	Good Clinical Practice
GH	Patient's Global Assessment of Disease Activity
GMS	Global Medical Safety
HAQ-DI	Health Assessment Questionnaire-Disability Index
HBsAg	hepatitis B surface antigen
HCQ	hydroxychloroquine

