3.2.3 Study Phases and Duration of Treatment

There will be 3 phases of this LTE study: Blinded active treatment, open-label treatment, and safety and efficacy follow-up.

CNTO 136 (sirukumab): Clinical Protocol CNTO136ARA3004 – Amendment 3

As described in Section 3.2.2, the blinded active treatment phase will continue until following 3 conditions have been met: the Week 52 DBL occurs in study CNTO136ARA3002, the Week 24 DBL occurs in study CNTO136ARA3003, and the last AI usability substudy subject completes the Week 16 visit or terminates from the study.

The open-label treatment phase of the study will begin after those 3 conditions have been met, and will continue through the last scheduled dose for all subjects. The safety and efficacy follow-up will include approximately 16 weeks of study evaluations following the last administration of study agent, including follow-up for patients who discontinued study treatment prior to their last scheduled dose. The safety and efficacy follow-up allows for monitoring of the subject for a period of equivalent to at least 5 times the half-life of sirukumab.

The maximum duration of the study is expected to be 156 weeks for subjects enrolling after participation in study CNTO136ARA3002 and 208 weeks for subjects enrolling after participation in study CNTO136ARA3003, followed by approximately 16 weeks of safety and efficacy follow-up after the administration of the final study agent injection of sirukumab.

After a minimum of 1 year treatment in CNTO136ARA3004 for subjects from study CNTO136ARA3002, or a minimum of 2 years of treatment in CNTO136ARA3004 for subjects from CNTO136ARA3003, and after sirukumab is approved for the treatment of RA in the subject's country of residence, the Sponsor may no longer offer study treatment in CNTO136ARA3004 for those specific subjects. At that point the subject will have the opportunity to discuss treatment options with their treating physician.

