8.2 Prohibited Medications

The use of the following drugs is not permitted concomitantly with SC study agent administration:

- Systemic immunosuppressives or DMARDs (other than MTX, SSZ, HCQ, CQ, and bucillamine) including azathioprine, oral cyclosporine A, tacrolimus, mycophenolate mofetil, leflunomide, oral or parenteral gold, and IL-1ra (anakinra)
- Biologic agents targeted at reducing TNF α (including but not limited to infliximab, golimumab, certolizumab pegol, etanercept, yisaipu, and adalimumab)
- Tocilizumab (anti IL-6 receptor)
- B-cell depleting agents (eg, rituximab)
- Cytotoxic drugs such as cyclophosphamide, chlorambucil, nitrogen mustard, or other alkylating agents
- Abatacept (ORENCIA[®])
- Tofacitinib (XELJANZ[®])
- Any other biologic therapy for the treatment of RA
- Investigational drugs

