11.2.1 Primary Endpoint

The number of subjects with each of the following long-term safety events through the end of study: cardiovascular SAEs, malignancies, serious infections, and gastrointestinal perforations will be summarized.

Serious cardiovascular events adjudicated by the CEC will be summarized by treatment group.

No hypothesis testing will be performed.

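### Primary safety events and laboratory grades after a switch to another biologic in follow-up are counted under the sirukumab group without being distinguished (minor)

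*Protocol*

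**What the plan says.** Scope of the restriction. Section 6.4 states: "Prohibited medications listed in Section 8.2 may not be initiated by subjects as long as they are receiving study agent administrations". Section 8.2 opens its list with "The use of the following drugs is not permitted concomitantly with SC study agent administration"; the list includes TNF blockers, tocilizumab, B-cell depleting agents, tofacitinib, cytotoxic drugs and "Any other biologic therapy for the treatment of RA". Section 4.3 asks subjects to keep to the "following prohibitions and restrictions during the course of the study", but its item 3 only refers back to Section 8.2. The drug restriction in its own words is item 5: "Must agree not to receive an investigational medical device or other investigational drugs".

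What happens on a switch. Section 10.2 item 13 makes starting a prohibited medication a reason for permanent discontinuation of study agent. The closing text of 10.2 keeps discontinued subjects in the Table 2 follow-up. A second route is local approval: under Section 3.2.3 the Sponsor may stop supplying study treatment after a minimum period, and "At that point the subject will have the opportunity to discuss treatment options with their treating physician". No waiting period is stated.

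What is counted. Section 11.2.1 summarises "The number of subjects with each of the following long-term safety events through the end of study", covering cardiovascular SAEs, malignancies, serious infections and gastrointestinal perforations. Section 11.2.2 summarises laboratory toxicity grade by treatment group over the same span. Section 11 analyses all enrolled subjects by previous study and treatment group, and Section 10.1 includes the 16 weeks in study completion. Section 11.8, by contrast, limits the general AE analysis to onset in the treatment phase, and Section 3.2.3 treats follow-up as a separate phase.

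**The concern.** The primary objective is long-term safety of sirukumab. Serious infection is a primary component, and neutrophils, platelets, hepatobiliary and lipid parameters form the major secondary endpoint. The agents that a subject may start in follow-up can affect the same outcomes: Section 1.1 itself links tocilizumab to serious infections and to hematologic, hepatobiliary and lipid abnormalities. A serious infection in follow-up Week 10 in a subject now on another immunosuppressant would be one more subject with an event in the 100 mg or 50 mg row, and a reader of the table could not tell. The two event windows compound this, because the same infection can be inside the primary count and outside the general AE tables.

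**Working it through.** The plan gives no event rate, sample size or switch rate for this point, so there is no figure of its own to reproduce. The check is a reading of the sections together, followed by simple arithmetic on time.

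**Is a switch allowed while the subject is still observed?**
- Sections 6.4 and 8.2 tie the restriction to study agent administration.
- Section 4.3 does not extend it, since item 3 defers to 8.2 and item 5 covers investigational products only. The same section does extend contraception and live-vaccine restrictions to 4 months after the last dose, so the protocol says so where it means a restriction to outlast dosing.
- Section 10.2 item 13, with its closing text, puts subjects who have started a prohibited drug into Table 2 follow-up.
- Marketed sirukumab is not named anywhere as a later treatment, but nothing excludes it after approval.

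**Are the later data in the group summaries?**
- Table 2 records adverse events and concomitant medications at all four visits (Weeks 4, 8, 12 and 16), and hematology, chemistry and lipids at Weeks 8 and 16.
- Sections 11.2.1 and 11.2.2 run to study end, and no text in Section 11 flags or separates data after a new agent.

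**How much time is at stake?** With T weeks on study treatment and 16 weeks of follow-up, the follow-up share of observed time is 16/(T + 16).
- 3002 completer, T = 156: 16/172 = 9.3%
- 3003 completer, T = 208: 16/224 = 7.1%
- 3002, earliest approval-driven stop, T = 52: 16/68 = 23.5%
- 3003, earliest approval-driven stop, T = 104: 16/120 = 13.3%
- Illustrative early stop at Week 28: 16/44 = 36.4%

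These shares assume that everyone switches on the first day of follow-up. If a fraction f switches at follow-up week w, the affected share is f × (16 − w)/(T + 16). The documents give neither f nor w, so the following are assumptions:
- T = 156: f = 10%, w = 0 gives 0.9%; f = 50%, w = 4 gives 3.5%; f = 100%, w = 0 gives 9.3%.
- T = 52: the same three cases give 2.4%, 8.8% and 23.5%.

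**Is study drug still present?** Section 3.2.3 says that follow-up covers at least 5 half-lives, so the half-life is at most 112/5 = 22.4 days. Residual drug is 2^(−days/half-life). At 22.4 days, 42% remains at Week 4, 18% at Week 8 and 3% at Week 16. At an assumed 14 days the figures are 25%, 6% and 0.4%. Overlap of sirukumab with a new agent is therefore plausible early in follow-up.

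**The case against.** The strongest reply is that counting every primary event to study end is the inclusive choice for safety, and a sound one while residual drug persists. That stands, and it is why no event should be removed. The trial is also descriptive, with no hypothesis, power calculation or randomised comparison, so no error rate is distorted. That stands too, and it limits the severity.

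Laboratory grades are summarised over time, so follow-up visits can be shown apart from on-treatment visits. This helps in part, but it does not separate switchers from others at the same visit. Causality assessment under Section 12.1.2 takes concomitant drugs into account, but the count in Section 11.2.1 is not restricted by attribution.

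The time shares do not measure an effect. They are ceilings, and the first weeks of follow-up include the last ordinary dosing interval.

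A reader might go further and infer that a switch spoils a planned washout, a reversibility assessment or a reading of disease activity off drug. The documents do not support that. Section 3.2.3 gives the purpose of follow-up as monitoring, none of these is an objective or endpoint, and Table 2 has no joint counts or HAQ-DI, so the composite scores cannot be derived in follow-up in any case. A reader might also infer that the antibody result needs a drug-free final sample. Pharm samples "will be collected at the final safety and efficacy follow up visit", but Section 9.3.3 classifies on any post-treatment sample and does not ask for one free of drug. Another company's biologic is not a source of antibodies to sirukumab, so only non-study sirukumab matters there.

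**Conclusion.** The point holds in limited form, as a minor one. Applied as written, the primary and laboratory windows credit events after a switch to the study dose group without distinguishing them, and the windows in Sections 11.2.1 and 11.8 do not agree. The affected share of observed time is at most 9.3% or 7.1% for completers and 23.5% or 13.3% at the earliest approval-driven stop. It can be larger for subjects who stop sooner, and the true share is unknown because the switch rate is not given. The conclusion rests on the protocol text. The SAP's content was not available for this check, so a handling rule there cannot be excluded and should be looked for first.

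**What to change.** This is a change to the analysis only; the rules on permitted and prohibited drugs stay as they are.

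1. Keep the count of all primary events through the end of the study as the main summary.
2. From the concomitant medication records, define for each subject the date of first use, after the last study injection, of any Section 8.2 agent or non-study sirukumab. For subjects discontinued under Section 10.2 item 13, use the date on which the prohibited agent was started.
3. Show primary events and follow-up laboratory grades before and after that date in separate labelled rows, by previous study and dose group, dropping none.
4. Reconcile the windows in Sections 11.2.1 and 11.8, stating for each summary whether follow-up onset counts.
5. For immunogenicity, only flag Week 16 follow-up samples taken after non-study sirukumab.

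The cost is analysis-plan wording and slightly more tabulation. Table 2 already collects concomitant medications at every follow-up visit, so no new data are needed. The drawback is that the after-switch rows will be sparse and should be read as description only.
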